**Table 5 Infusion Reaction Treatment Guidelines**

NCI CTCAE Grade	Treatment	Premedication at subsequent dosing

Grade 1 Mild reaction; infusion interruption not indicated; intervention not indicated
	
Increase monitoring of vital signs as medically indicated until the subject is deemed medically stable in the opinion of the investigator.
	
None

Grade 2 Requires infusion interruption but responds promptly to symptomatic treatment (e.g., antihistamines, NSAIDS, narcotics, IV fluids); prophylactic medications indicated for < =24 hrs
	
Stop Infusion and monitor symptoms. Additional appropriate medical therapy may include but is not limited to:                      IV fluids                      Antihistamines                      NSAIDS                      Acetaminophen                      Narcotics
 
Increase monitoring of vital signs as medically indicated until the subject is deemed medically stable in the opinion of the investigator.                      If symptoms resolve within one hour of stopping drug infusion, the infusion may be restarted at 50% of the original infusion rate (e.g., from 100 mL/hr to 50 mL/hr). Otherwise dosing will be held until symptoms resolve and the subject should be premedicated for the next scheduled dose.
 
Subjects who develop Grade 2 toxicity despite adequate premedication should be permanently discontinued from further trial treatment administration.
	
Subject may be premedicated 1.5h (± 30 minutes) prior to infusion of pembrolizumab (MK-3475) with:
 
Diphenhydramine 50 mg po (or equivalent dose of antihistamine).
 
Acetaminophen 500-1000 mg po (or equivalent dose of antipyretic).


Grades 3 or 4
 
Grade 3: Prolonged (i.e., not rapidly responsive to symptomatic medication and/or brief interruption of infusion); recurrence of symptoms following initial improvement; hospitalization indicated for other clinical sequelae (e.g., renal impairment, pulmonary infiltrates)
 
Grade 4: Life-threatening; pressor or ventilatory support indicated
	
Stop Infusion. Additional appropriate medical therapy may include but is not limited to:                      IV fluids                      Antihistamines                      NSAIDS                      Acetaminophen                      Narcotics                      Oxygen                      Pressors                      Corticosteroids                      Epinephrine
 
Increase monitoring of vital signs as medically indicated until the subject is deemed medically stable in the opinion of the investigator.                      Hospitalization may be indicated.  Subject is permanently discontinued from further trial treatment administration.
	
No subsequent dosing

Appropriate resuscitation equipment should be available in the room and a physician readily available during the period of drug administration.
		

### 5.7.2 Procedures for Subjects Exhibiting Serotonin Syndrome

As noted in the background, there is a theoretical chance that Epacadostat/INCB024360 could cause an increase in serotonin levels in the brain that might trigger SS (*Boyer and Shannon 2005*) when administered in combination with other serotonergic agents. This syndrome has been most closely associated with use of MAOIs, Demerol®, linezolid, or methylene blue; all of these agents are prohibited during the study. Serotonin reuptake inhibitors (SSRIs) and serotonin/norepinephrine reuptake inhibitors (SNRIs) are permitted in the study. The following procedures will be implemented if subjects exhibit the signs/symptoms of SS described, including tremor; hyperreflexia; spontaneous, ocular, or inducible clonus; together with agitation, fever, diaphoresis, or muscle rigidity:

- Immediately interrupt Epacadostat/INCB024360 administration. Administration of Pembrolizumab/MK-3475 may continue.
- Immediately interrupt any SSRI or SNRI administration.
  - Provide appropriate medical management of the subject until all signs/symptoms are resolved (eg, IV fluids and/or sympathomimetic amines for hypotension, benzodiazepines for agitation, administration of 5-hydroxytryptamine antagonists such as cyproheptadine).
  - If subject chooses to remain in the study, restart treatment with INCB024360 after the SSRI or SNRI has been discontinued, no sooner than 5 half-lives have elapsed for the specific SSRI or SNRI in question, and after resolution of signs/symptoms of SS. The SSRI or SNRI dosing MAY NOT be restarted.
  - If subject chooses to withdraw from the study, or must restart treatment with SSRI or SNRI, the subject should be scheduled for a follow-up visit. Treatment with SSRI or SNRI may be initiated 2 weeks after resolution of signs and symptoms of SS.

### 5.7.3 Treatment After Initial Evidence of Radiologic Evidence of Disease Progression

Immunotherapeutic agents such as Pembrolizumab (MK-3475) and Epacadostat (INCB024360) may produce antitumor effects by potentiating endogenous cancer-specific immune responses. The response patterns seen with such as approach may extend beyond the typical time course of responses seen with cytotoxic agents and can manifest as a clinical response after an initial increase in tumor burden or even the appearance of new lesions.

If radiologic imaging shows PD, tumor assessment should be repeated  $\geq 4$  weeks later to confirm PD, with the option of continuing treatment per below while awaiting radiologic confirmation of progression. If repeat imaging shows a reduction in the tumor burden compared to the initial scan demonstrating PD, treatment may be continued as per treatment calendar. If repeat imaging confirms PD, subjects will be discontinued from study therapy. In determining whether the tumor burden has increased or decreased, investigators should consider all target lesions as well as non-target lesions.

When feasible, subjects should not be discontinued until progression is confirmed; however, the decision to continue study treatment after the first evidence of disease progression is at the investigator's discretion based on the clinical status of the subject as described in [Table 6](#).

Subjects may receive study treatment while waiting for confirmation of PD if they are clinically stable as defined by the following criteria:

- Absence of signs and symptoms (including worsening of laboratory values) indicating disease progression.
- No decline in ECOG performance status.
- Absence of rapid progression of disease.
- Absence of progressive tumor at critical anatomical sites (e.g., cord compression) requiring urgent alternative medical intervention.

**Table 6: Imaging and Treatment After First Radiologic Evidence of Progressive Disease**

	Clinically Stable		Clinically Unstable	
	Imaging	Treatment	Imaging	Treatment
First radiologic evidence of PD	Repeat imaging at $\geq 4$ weeks to confirm PD	May continue study treatment at the investigator's discretion while awaiting confirmatory scan	Repeat imaging at $\geq 4$ weeks to confirm PD if possible	Discontinue treatment
Repeat scan confirms PD	No additional imaging required	Discontinue treatment	No additional imaging required	N/A
Repeat scan shows SD, PR, or CR	Continue regularly scheduled imaging assessments every 9 weeks	Continue study treatment at the investigator's discretion	Continue regularly scheduled imaging assessments every 9 weeks	May restart study treatment if condition has improved and/or clinically stable per investigator's discretion

## **5.8 Diet/Activity/Other Considerations**

### **5.8.1 Diet**

Subjects should maintain a normal diet unless modifications are required to manage an AE such as diarrhea, nausea or vomiting.

### **5.8.2 Contraception**

Pembrolizumab and epacadostat may have adverse effects on a fetus in utero. Furthermore, it is not known if pembrolizumab has transient adverse effects on the composition of sperm. Non-pregnant, non-breast-feeding women may be enrolled if they are willing to use 2 methods of birth control or are considered highly unlikely to conceive. Highly unlikely to conceive is defined as 1) surgically sterilized, or 2) postmenopausal (a woman who is  $\geq 45$  years of age and has not had menses for greater than 1 year will be considered postmenopausal), or 3) not heterosexually active for the duration of the study. The two birth control methods can be either two barrier methods or a barrier method plus a hormonal method to prevent pregnancy. Subjects should start using birth control from study Visit 1 throughout the study period up to 120 days after the last dose of study therapy.

The following are considered adequate barrier methods of contraception: diaphragm, condom (by the partner), copper intrauterine device, sponge, or spermicide. Appropriate hormonal contraceptives will include any registered and marketed contraceptive agent that contains an estrogen and/or a progestational agent (including oral, subcutaneous, intrauterine, or intramuscular agents).

Subjects should be informed that taking the study medication may involve unknown risks to the fetus (unborn baby) if pregnancy were to occur during the study. In order to participate in the study they must adhere to the contraception requirement (described above) for the duration of the study and during the follow-up period. If there is any question that a subject will not reliably comply with the requirements for contraception, that subject should not be entered into the study.

### **5.8.3 Use in Pregnancy**

If a subject inadvertently becomes pregnant while on treatment with pembrolizumab, the subject will immediately be removed from the study. The site will contact the subject at least monthly and document the subject's status until the pregnancy has been completed or terminated. The outcome of the pregnancy will be reported to the Sponsor and to Merck/Incyte without delay and within 24 hours to the Sponsor and within 2 working days to Merck/Incyte, as described in section 10.7, if the outcome is a serious adverse experience (e.g., death, abortion, congenital anomaly, or other disabling or life-threatening complication to the mother or newborn).

The study investigator will make every effort to obtain permission to follow the outcome of the pregnancy and report the condition of the fetus or newborn to the Sponsor. If a male subject impregnates his female partner the study personnel at the site must be informed immediately and the pregnancy reported to the Sponsor and to Merck/Incyte and followed as described above and in Section 7.2.2.

#### **5.8.4 Use in Nursing Women**

It is unknown whether pembrolizumab is excreted in human milk. Since many drugs are excreted in human milk, and because of the potential for serious adverse reactions in the nursing infant, subjects who are breast-feeding are not eligible for enrollment.

#### **5.9 Subject Withdrawal/Discontinuation Criteria**

Subjects may withdraw consent at any time for any reason or be dropped from the trial at the discretion of the investigator should any untoward effect occur. In addition, a subject may be withdrawn by the investigator or the Sponsor if enrollment into the trial is inappropriate, the trial plan is violated, or for administrative and/or other safety reasons. Specific details regarding discontinuation or withdrawal are provided in Section 7.1.4 – Other Procedures.

A subject must be discontinued from the trial for any of the following reasons:

- The subject or legal representative (such as a parent or legal guardian) withdraws consent.
- Confirmed radiographic disease progression (=2nd scan within 4-8 weeks)

*Note:* For unconfirmed radiographic disease progression, please see Section 5.7.3

*Note:* A subject may be granted an exception to continue on treatment with confirmed radiographic progression if clinically stable or clinically improved, please see Section 5.7.3

- Unacceptable adverse experiences as described in Section 5.2.1.2
- Intercurrent illness that prevents further administration of treatment
- Investigator's decision to withdraw the subject
- The subject has a confirmed positive serum pregnancy test
- Noncompliance with trial treatment or procedure requirements
- The subject is lost to follow-up
- Completed 12 months of uninterrupted treatment with pembrolizumab or 18 administrations of study medication, whichever is later.

- Administrative reasons

The End of Treatment and Follow-up visit procedures are listed in Section 6 (Protocol Flow Chart) and Section 7.1.5 (Visit Requirements). After the end of treatment, each subject will be followed for 30 days for adverse event monitoring (serious adverse events will be collected for 90 days after the end of treatment as described in Section 7.2.3.1). Subjects who discontinue for reasons other than progressive disease will have post-treatment follow-up for disease status until disease progression, initiating a non-study cancer treatment, withdrawing consent or becoming lost to follow-up. After documented disease progression each subject will be followed by telephone for overall survival until death, withdrawal of consent, the end of the study, or 2 years beyond the last administration of study drug, whichever occurs first.

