### **5.3.6 Timing of Dose Administration of Pembrolizumab.**

Combination treatment (during treatment period) should be administered on Day 1 of each cycle after all procedures/assessments have been completed as detailed on the Trial Flow Chart (Section 6.0). Trial treatment may be administered up to 3 days before or after the scheduled Day 1 of each cycle due to administrative reasons.

→ All trial treatments will be administered on an outpatient basis.

Pembrolizumab 200 mg will be administered as a 30-minute IV infusion every 3 weeks until disease progression, unacceptable toxicity, or up to 24 months in patients without disease progression. . Sites should make every effort to target infusion timing to be as close to 30 minutes as possible. However, given the variability of infusion pumps from site to site, a window of -5 minutes and +10 minutes is permitted (i.e., infusion time is 30 minutes: -5 min/+10 min).

The Pharmacy Manual contains specific instructions for the preparation of the pembrolizumab infusion fluid and administration of infusion solution.

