***If clinically indicated tissue from a biopsy will also be banked using the UCCCC# 8980 banking protocol.***

**2. -- 2 Purple top tubes, blood volume, processing etc will follow HTRC SOPs**

**3. – PAXgene tube, blood volume, processing etc will follow HTRC SOPs**

**\* Treatment cycle length = 21 days**

**\*\* After cycle 8, as clinically appropriate ECOG performance status, physical exam, and adverse event recording interval may be increased to every other cycle (=every 6 weeks).**

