**End of Treatment = end of 2 years of treatment OR progressive disease as outlined in prior section.**

**Survival follow-up** can be done via phone if patient is not coming in for additional care

*Laboratory tests for screening or potentially a Second Treatment Course should be performed within 14 days prior to the first dose of treatment. After Cycle 1, pre-dose laboratory procedures can be conducted up to 72 hours prior to dosing.*

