### **7.2.7 Other Procedures**

#### **7.2.7.1 Withdrawal/Discontinuation**

When a subject discontinues/withdraws prior to trial completion, all applicable activities scheduled for the final trial visit should be performed at the time of discontinuation. Any adverse events, which are present at the time of discontinuation/withdrawal should be followed in accordance with the safety requirements outlined in Section 7.2 - Assessing and Recording Adverse Events. Subjects who a) attain a CR or b) complete 24 months of treatment with pembrolizumab may discontinue treatment with the option of restarting treatment if they meet the criteria specified in Section 7.1.5.5. After discontinuing treatment following assessment of CR, these subjects should return to the site for a Safety Follow-up Visit (described in Section 7.1.5.3.1) and then proceed to the Follow-Up Period of the study (described in Section 7.1.5.4).

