### **7.2.8.3 Treatment Period**

Treatment period is 2 years or until progression.

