#### **7.2.8.6 Second Course Phase (Retreatment Period)**

Subjects who stop pembrolizumab/epacadostat with SD or better may be eligible for up to one year of additional therapy with pembrolizumab + epacadostat if they progress after stopping study treatment. This retreatment is termed the Second Course Phase of this study and is only available if the study remains open and the subject meets the following conditions:

- **Either**

- Stopped initial treatment with pembrolizumab + epacadostat after attaining an investigator-determined confirmed CR according to RECIST 1.1, and
  - Were treated for at least 24 weeks with pembrolizumab + epacadostat before discontinuing therapy
  - Received at least two treatments with pembrolizumab and concurrent epacadostat (during that timeframe) beyond the date when the initial CR was declared

**OR**

- Had SD, PR or CR and stopped pembrolizumab/epacadostat treatment after 24 months of study therapy for reasons other than disease progression or intolerability

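### Section 5.9 requires treatment to stop at about 12 months (18 doses), while five other places set or assume 24 months (35 doses)

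*Combined protocol and SAP*

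**What the plan says.** All references are to the combined protocol and SAP.

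- Section 5.9, in the list of reasons that oblige the investigator to discontinue a subject: "Completed 12 months of uninterrupted treatment with pembrolizumab or 18 administrations of study medication, whichever is later".
- Section 5.3.6, on pembrolizumab dosing: "every 3 weeks until disease progression, unacceptable toxicity, or up to 24 months in patients without disease progression".
- Notes to the flow chart in section 6.1: "End of Treatment = end of 2 years of treatment OR progressive disease as outlined in prior section". The same notes give the cycle: "Treatment cycle length = 21 days".
- Section 7.2.8.3: "Treatment period is 2 years or until progression".
- Section 7.2.7.1 refers to subjects who "complete 24 months of treatment with pembrolizumab may discontinue treatment with the option of restarting treatment".
- Section 7.2.8.6 offers a second course by two routes. One needs a confirmed complete response. The other is for patients with SD, PR or CR who "stopped pembrolizumab/epacadostat treatment after 24 months of study therapy for reasons other than disease progression or intolerability". The second course "is only available if the study remains open and the subject meets the following conditions".

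**The concern.** The 5.9 list is mandatory and any single entry is enough. One entry ends treatment at about one year. Three other places state a two-year period, and two more are written as though patients will reach it. An investigator cannot comply with both: giving dose 19 to a patient on schedule breaches 5.9, and withholding it from a patient who is not progressing cuts short the period defined in 6.1 and 7.2.8.3.

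At stake are treatment, exposure and cumulative toxicity after month 12 in patients who are doing well, and their access to retreatment. Duration of response and the later part of the PFS and OS curves would then be observed under whichever limit was applied.

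**Working it through.** **Inputs.** Cycle length is 21 days (notes to 6.1). The limits come from 5.9 (12 months, 18 administrations) and from 5.3.6, 6.1 and 7.2.8.3 (24 months or 2 years). I take 12 months as 365 days and 24 months as 730 days, and vary both below. With the first dose on day 0 and no interruption, dose k falls on day (k − 1) × 21.

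**1. The plan's own pairing of 12 months with 18 administrations.**
- Dose 18: 17 × 21 = day 357.
- Dose 19: 18 × 21 = day 378.
- Exactly 18 doses fit within 365 days, so the pairing reproduces. The later of day 357 and day 365 is day 365. The 5.9 rule takes effect then and dose 19 is not given.

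**2. The 24-month limit.**
- Dose 35: 34 × 21 = day 714.
- Dose 36: 35 × 21 = day 735, past day 730.
- So 35 doses are given.

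**3. Difference.** 35 − 18 = 17 doses; 35 / 18 = 1.94; 730 − 365 = 365 days.

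**4. Sensitivity.** Taking 12 months as anything from 360 to 366 days still gives 18 doses, and 24 months as 720 to 731 days still gives 35. The 3-day dosing window in 5.3.6 does not alter this: 378 − 3 = 375, beyond 366, and 735 − 3 = 732, beyond 731.

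**5. Second course.** Take a patient with SD or PR stopped under 5.9 on day 365. The first route in 7.2.8.6 fails because there is no complete response. The second fails because 12 months is short of 24. A patient with a confirmed complete response may still qualify by the first route.

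**6. What the conflict does not reach.**
- *1-year landmarks.* The first dose withheld would have fallen on day 378, after day 365.
- *Simon design.* With 10 patients in stage 1 (stop if no response), 15 in total and rejection at 2 or more responses, the exact calculation gives a type I error of 0.0667 at a 3% response rate and power of 0.805 at 20%. Both agree with section 8.1, and treatment duration enters neither.
- *Response rate.* Only a first response appearing after month 12 could be lost.
- *Follow-up.* Sections 5.9 and 7.2.8.5 keep following disease status after treatment stops for reasons other than progression.

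**7. How many patients.** The documents give no count, only two planning figures.
- Section 4.2.4.1 expects about 30% alive at one year. On 30 patients that is 0.30 × 30 = 9 alive, and those still on drug without progression would be fewer.
- Section 1.0 estimates 18 months of enrolment and a 24-month trial. On that timetable the last patient enrolled has 24 − 18 = 6 months, and only patients enrolled at the very start could approach 24 months of treatment.

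**The case against.** Three defences deserve an answer.

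- *The 24 months is only a ceiling.* That could be said of 5.3.6 alone. It does not fit 6.1 or 7.2.8.3, which define the treatment period itself.
- *Taking the later of the two conditions removes the conflict.* It does not for a patient dosed on schedule, because both conditions are met by day 365. A patient with missed doses could remain on drug longer under 5.9, so the point is confined to uninterrupted dosing.
- *The practical effect is small.* This largely stands. The planning figures suggest that few patients reach month 12 on treatment, and the second course may scarcely arise if the study closes near its estimated end. Both figures are estimates, however. The suboptimal benefit cohort enters with ongoing stable disease and may do better than 30% alive at one year, and the follow-up in 5.9 and 7.2.8.5.1 can run beyond 24 months.

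A reader might also infer more than the documents support:

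- *That different sites would treat similar patients differently.* Sections 10.2 and 10.6 describe a study intended for a single center. Affiliate wording survives elsewhere, but it is weak ground for a between-site argument.
- *That a dose hold restarts the 12 months because 5.9 requires uninterrupted treatment.* The protocol does not say how holds count, and no section states a restart rule. Dose counts built on that reading would be speculation.
- *That the primary result is compromised.* Step 6 of the working shows that it is not.

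**Conclusion.** The inconsistency is real and nothing in the documents resolves it. Section 5.9 is wrong as written against the rest of the protocol. Neither 12 nor 24 months is being criticized as a design. For a patient on uninterrupted 21-day dosing the two limits differ by 17 doses, about a year. For a patient with SD or PR, obeying 5.9 also removes eligibility for the second course while the study is open.

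The dose counts assume a first dose on day 0 and no holds, and they are stable to how months are converted to days. The number of patients affected is unknown and probably small. The point should be fixed because the rule is mandatory and governs treatment, but it does not bear on the primary inference.

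**What to change.** The sponsor should first confirm which duration is intended.

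**If 24 months,** replace the 5.9 bullet with: *Completed 24 months of treatment with pembrolizumab, counted by calendar from the first dose and including any dose holds (at most 35 three-weekly administrations).* This agrees with 5.3.6, the notes to 6.1, 7.2.7.1, 7.2.8.3 and 7.2.8.6. It counts pembrolizumab, as 5.3.6 and 7.2.7.1 do, and it settles how holds are treated.

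**If 12 months,** amend those five places instead, including the 24-month condition for the second course, and state in 5.9 how holds count.

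The first option costs one bullet in a protocol amendment. It adds no patients, and no visits or procedures beyond the treatment period already stated elsewhere. If the working intention has been 12 months, though, adopting 24 would mean up to 17 further infusions for each patient who does not progress, which is why intent should be settled first.
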